4.6. Missing Data Handling and Imputation Rules

No missing safety and reactogenicity results will be imputed. Incomplete AE onset and end dates will be imputed according to the rules specified in [Appendix 2](#). For safety analysis, percentages will be based on the analysis set of interest (e.g., Safety Set) within each treatment group and overall for the relevant vaccination/period of interest. For reactogenicity analysis, the denominator will be number of participants in the reactogenicity analysis set for the relevant vaccination/period of interest.

Any immunogenicity results that are below the limit of detection (LOD) or lower limit of quantification (LLOQ) will be imputed as half of the corresponding limit and results above the upper limit of quantification will be imputed as that limit for analysis purposes.

5. Participant Disposition and Protocol Deviations

5.1. Participant Disposition

The number and percentage of participants in the following categories (analysis sets defined in [Section 4.4](#)) will be summarized based on the following (where applicable):

- Randomized Set
- Intent-to-Treat Set
- Modified Intent-to-Treat Set (mITT)
- Per-Protocol Set (PP)
- Cell Mediated Immunity Analysis Subsets (CMI)
 - mITT-CMI
 - PP-CMI
- Safety Set

- Reactogenicity Set (Dose 1)
- Reactogenicity Set (Dose 2)
- Booster Randomized Set
- Booster Safety Set
- Booster Reactogenicity Set
- Booster Intent-to-Treat Set (Booster ITT)
- Booster Modified Intent-to-Treat Set (Booster mITT)
- Booster Per-Protocol Set (PP)
- Booster Cell Mediated Immunity Subset (Booster CMI)
 - Booster mITT-CMI
 - Booster PP-CMI

The number of participants in the following categories will be summarized based on participants screened:

- Number of participants screened
- Number and percentage of screen failure participants and the reason for screen failure

The number and percentage of participants in each of the following disposition categories will be summarized based on the Randomized set for the priming vaccination period:

- Received each dose of study vaccine for priming vaccination dose 1 and dose 2
- Prematurely discontinued before receiving the second dose of study vaccine and the reason for discontinuation
- Prematurely discontinued before receiving the booster dose of study vaccine and the reason for discontinuation
- Completed study
- Prematurely discontinued the study and the reason for discontinuation

A participant disposition listing will be provided, including informed consent, participants who completed the study injection schedule, participants who completed study, participants who discontinued from study vaccine or who discontinued from participation in the study, with reasons for discontinuation. Randomization data will be also provided in a listing.

A table summarizing the frequencies and percentages for the following will be provided by the primary vaccination treatment groups for Safety Analysis set:

- Participants who have completed booster vaccination and who are followed for 56 days post booster vaccination or less
- Participants who have completed booster vaccination and who have been followed longer (> 56 days but < 180 days after booster dose)
- Participants who have completed primary vaccination and who have been followed < 12 months

A table summarizing the frequencies and percentages for the following will be provided by the primary vaccination treatment groups for re-enrolled Safety Analysis set:

- Participants who have completed primary vaccination and who have re-enrolled and with follow-up < 12 months
- Participants who have completed primary vaccination, who have re-enrolled and who have received a booster dose with follow-up > 56 days but < 180 days.

A separate listing will be provided for screen failure participants with reasons for screen failure.

For re-enrolled subjects, disposition will be summarized and listed separately based on the Randomized set. For the booster vaccination period, the number of participants randomized to booster and the number of participants in the Booster Safety and Booster Reactogenicity sets will be summarized.

5.2. Protocol Deviations

A protocol deviation is any change, divergence, or departure from the study design or procedures defined in the protocol. Deviations are classified as significant or non-significant based on the following definition:

- A significant protocol deviation affects primary efficacy and safety assessments, the safety or mental integrity of a participant, or the scientific value of the trial/project.
- A major protocol deviation is defined as a deviation that affects primary immunogenicity assessments and results in subject being removed from per-protocol analysis set.

Protocol deviations will be documented by the clinical monitor throughout the course of monitoring visits. The investigator will be notified in writing by the monitor of deviations. The human research ethics committee/IRB should be notified of all protocol deviations, if

appropriate, in a timely manner. Protocol deviations will be reviewed prior to any formal analyses.

Significant and major protocol deviations will be summarized (separately) by deviation type (e.g., missed assessment) and subtype for the Randomized analysis set. Only significant and major PDs are summarized. Reasons for exclusion from PP Set and Booster PP Set (e.g., major protocol deviations, no assigned dose of assigned study vaccine within the predefined window, no blood collection with valid immunogenicity results within the predefined window) will also be summarized for the Randomized analysis set and Booster Randomized analysis set, respectively.

All protocol deviations will be presented in a data listing. A separate listing of all protocol deviations for re-enrolled Randomized analysis set will also be provided. Details of admission criteria deviations will be presented in a separate data listing.

6. Demographics and Baseline Characteristics

6.1. Demographics

Descriptive statistics will be calculated for the following continuous demographic and baseline characteristics: age (years), weight (kg), height (cm), body mass index (BMI) (kg/m²). The number and percentage of participants will be provided for categorical variables such as age group, sex, race, ethnicity, country, site, baseline SARS-CoV-2 serostatus (positive/negative/missing) defined by nucleocapsid testing at Day 0, and evidence of viral shedding as measured by a saliva RT-PCR test at Baseline.

Baseline SARS-CoV-2 serostatus is defined as SARS CoV-2 nucleocapsid (N) antibody level of greater or equal to 5000 (AU/mL). This threshold is defined by BioA laboratories based on levels for a clinical definition of PCR-confirmed COVID-19 infection.

The number and percentage of participants will be summarized by site and by stratification factor at randomization (i.e., ≥ 18 to <56 years; ≥ 56 years) separately based on the Safety set for the priming vaccination period, re-enroll subjects, and booster vaccination period.

Summaries will be provided separately based on the Safety set, mITT set, PP set, mITT-CMI subset by study treatment group. The summaries will be repeated by study treatment group for re-enrolled subjects based on Safety set and for the booster vaccination period based on the Booster Safety set, Booster mITT set, Booster PP set, Booster mITT-CMI subset. Summary of demographics by ≥ 18 to <65 years vs. ≥ 65 years will also be provided for the priming vaccination period.

For screened failure participants, age (years), gender, race and ethnicity will be presented in a listing.

6.2. Medical History

Medical history will be coded using MedDRA version 23.0 or higher.

The number and percentage of participants with any medical history will be summarized by SOC and PT based on Safety Set. A participant will be counted only once for multiple events within each SOC and PT. SOC will be displayed in internationally agreed order. Medical history will also be presented in a data listing.

7. Treatments and Medications

7.1. Prior and Concomitant Medications

Prior and concomitant medications and non-study vaccinations will be coded using the WHO drug dictionary (WHODrug-Global-B3 202003). The summary of concomitant medications will be based on the Safety set (separate summary will also be provided for the Booster Safety Set). Categorization of prior, concomitant, and post medications is summarized in [Appendix 2](#).

The number and percentage of participants using concomitant medications will be summarized by study treatment group as follows:

- All concomitant medications overall for priming vaccination period, concomitant medications within 7 days after either priming dose of study vaccine, and concomitant medications within 28 days after either priming dose of study vaccine
- All concomitant medications taken through 7 days after each priming dose of study vaccine separately
- All concomitant medications overall for booster vaccination period, concomitant medications within 7 days after booster dose of study vaccine, and concomitant medications within 28 days after booster dose of study vaccine.

For re-enrolled subjects, similar summaries as above will be performed for the priming vaccination period only.

Prior, concomitant and post medications will be presented in a listing.

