5.10.1 Concomitant Therapy

Study site staff must question the participant regarding any medications taken and vaccinations received by the participant and record the following information in the eCRF:

- All non-study vaccinations administered within the period starting 28 days before the first dose of study vaccine.
- All concomitant medications taken through 28 days after each dose of study vaccines.
- All non-study vaccinations received at any point in the study.
- Any concomitant medications used to prevent or treat COVID-19.
- Any concomitant medications relevant to or for the treatment of an SAE, an NOCD, an MAAE, or an AE leading to discontinuation/withdrawal.
- Participant will be asked in the Diary if they have taken any antipyretic or analgesic to treat or prevent fever or pain within 7 days after each study vaccine administration, including the day of dosing. Reported antipyretic or analgesic medications should be recorded in the source document by the site staff during the study visits or via other participant interactions (eg, telephone calls).

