13.2. Appendix 2: Imputation Rules

13.3. Missing Dates of Prior/Concomitant Medications and Non-Study Vaccinations

Imputation rules for missing or partial start/stop dates of medication are defined below:

- Missing or partial medication start date:
 - If only Day is missing, use the first day of the month, unless:
 - The medication end date is on/after the date of first injection or is missing/partial AND the start month and year of the medication coincide with the start month and year of the first injection. In this case, use the date of first injection.
 - If Day and Month are both missing, use the first day of the year, unless:
 - The medication end date is on/after the date of first injection or is missing/partial AND the start year of the medication coincide with the start year of the first injection. In this case, use the date of first injection.
 - If Day, Month, and Year are all missing, the date will not be imputed, but the medication will be treated as though it began prior to the first injection for purposes of determining if status as prior or concomitant.
- Missing or partial medication stop date:
 - If only Day is missing, use the earliest date of (last day of the month, study completion, discontinuation from the study, or death).
 - If Day and Month are both missing, use the earliest date of (last day of the year, study completion, discontinuation from the study, or death).
 - If Day, Month, and Year are all missing, the date will not be imputed, but the medication will be flagged as a continuing medication.

In summary, the prior, concomitant or post categorization of medications and non-study vaccinations is described in **Table 13-2** below.

Table 13-2: Prior, Concomitant, and Post Categorization of Medications and Non-study Vaccinations

Medication Start Date	Medication Stop Date				
	< First Injection Date of IP	≥ First Injection Date and ≤ 28 Days After Day 28 Injection	> 28 days after Second injection to Third (Booster) injection or Early Termination for subjects without Third injection	≥ Third injection date and ≤ 28 days after Third injection	> 28 days after Third Injection [2]
< First injection date of IP [1]	P	P	P	P	P
≥ First injection date and ≤ 28 days after Second injection	-	C	C	C	C
> 28 days after Second injection to Third (Booster) injection or Early Termination for subjects without Third injection	-	-	A	A	A
≥ Third injection date and ≤ 28 days after Third injection	-	-	-	C	C
> 28 days after Third Injection	-	-	-	-	A

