A: Post; C: Concomitant; P: Prior

[1] includes medications with completely missing start date

[2] includes medications with completely missing end date

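### SAP Table 13-2 labels medications by start date alone, so the 7-day and 28-day concomitant-medication tables leave out drugs that were already in use and still being taken

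*SAP*

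**What the plan says.** SAP 7.1 counts participants using concomitant medications by study treatment group. It does so for each vaccination period overall and for 7-day and 28-day windows after dosing. One table is described as "All concomitant medications taken through 7 days after each priming dose of study vaccine separately". Section 7.1 does not itself define the class: "Categorization of prior, concomitant, and post medications is summarized in" Appendix 2. Drugs classed as prior or post go to a listing and have no summary.

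Table 13-2 in Appendix 2 crosses start-date rows with stop-date columns and assigns one of three labels: "A: Post; C: Concomitant; P: Prior". No label combines prior and concomitant. The third row reads "> 28 days after Second injection to Third (Booster) injection or Early Termination for subjects without Third injection" and carries A wherever it has an entry.

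For a completely missing start date, SAP 13.3 says that "the medication will be treated as though it began prior to the first injection for purposes of determining if status as prior or concomitant". Note 1 to the table places such drugs in the first row, which is P throughout. A start date lacking only the day is set to the date of dose 1 when "The medication end date is on/after the date of first injection or is missing/partial AND the start month and year of the medication" match those of dose 1. A parallel rule covers a start date with only the year.

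Protocol 5.10.1 collects drugs by use: "All concomitant medications taken through 28 days after each dose of study vaccines".

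**The concern.** The protocol collects drugs taken in the windows, and SAP 7.1 describes its tables in the same terms. Table 13-2 instead selects drugs by when they were started. A participant on a daily drug since before enrolment takes it in every post-dose window, yet is counted in none of them on account of that drug. Such drugs are foreseeable. Protocol 4.1.2 admits people with well-controlled mild or moderate comorbidities, and half the planned sample is aged 56 or over.

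What is at stake is whether a descriptive safety table shows what its description says. A reader would take the percentages as drug use after vaccination, when they are closer to drugs newly started on study.

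**Working it through.** The plan gives no medication rates and no figure of its own to reproduce. The check is therefore to apply the stated rules.

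**Step 1: the grid.** Table 13-2 in short form (D1, D2 and D3 are the two priming doses and the booster):

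| Start \ Stop | before D1 | D1 to D2+28 | after D2+28, to D3 | D3 to D3+28 | after D3+28 |
|---|---|---|---|---|---|
| before D1, or missing | P | P | P | P | P |
| D1 to D2+28 | – | C | C | C | C |
| after D2+28, to D3 | – | – | A | A | A |
| D3 to D3+28 | – | – | – | C | C |
| after D3+28 | – | – | – | – | A |

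All 5 rows carry a single label, so the stop date never changes the class.

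**Step 2: cells that overlap a post-dose block.**
- Priming block (D1 to D2+28): rows 1–2 by columns 2–5 gives 2 × 4 = 8 cells. Four are not C, all of them P.
- Booster block (D3 to D3+28): rows 1–4 by columns 4–5 gives 4 × 2 = 8 cells. Four are not C: two P and two A.

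**Step 3: example drugs, doses on Days 0, 28 and 208.**

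| Drug taken | Label | Effect on tables |
|---|---|---|
| Day −30, ongoing | P | left out of all six windows (7 and 28 days after each of three doses) |
| Day −1 to Day 3 | P | left out of both dose 1 windows |
| Day 100, ongoing | A | left out of both booster windows |
| Day 207 to Day 212 | A | left out of both booster windows |
| Day 1 to Day 3 | C | counted |
| Day 25 to Day 32 | C | counted |

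**Step 4: incomplete dates.** Assume, for illustration, dose 1 on 10 Feb 2021, dose 2 on 10 Mar 2021 and the booster on 6 Sep 2021. For a drug still in use after the booster:
- Start 5 Feb 2021, complete: P.
- Start Feb 2021, day unknown: set to 10 Feb, so C.
- Start 2021, day and month unknown: set to 10 Feb, so C.
- Start Jan 2021, day unknown: set to 1 Jan, so P.
- Start completely missing: P.

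A less complete date can therefore get a drug counted when a complete one does not. The opposite error also occurs. Take a drug recorded as starting and stopping in Feb 2021, both days unknown, that really ended on 6 Feb. The start becomes 10 Feb. The stop becomes the last day of February, unless study completion, discontinuation or death came earlier. The drug is labelled C and falls in the 7-day window after dose 1, although it was never taken there. A completely missing stop date is flagged as continuing, which can also overcount.

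**Step 5: size per omitted participant.**
- Priming arm, planned: 600/4 = 150; 1/150 = 0.67 points.
- Priming arm, from the 579 enrolled (Protocol 1.5): 579/4 = 144.75; 1/144.75 = 0.69 points.
- Booster groups as pooled in SAP Table 4-1, at planned numbers and ignoring attrition and re-enrolment: ARCT-primed 450/4 = 112.5, so 0.9 points; placebo-primed 150/3 = 50, so 2.0 points.
- Lowest booster group size in SAP 4.2: 1/25 = 4.0 points.

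**The case against.** The best defence is that little depends on these tables. The label feeds no endpoint or estimand. Immune-modifying drugs are identified by medical review (SAP Appendix 3, IcEv3), and major deviations for the per-protocol set are judged by the Sponsor Medical Monitor in a blinded manner. The omitted records stay in the listing. All of this stands, and it makes the point minor. It does not make the tables match their description.

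Several stronger readings are tempting, and the documents do not support them.

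- A reader might infer that the counts can only be too low. That holds for drugs with complete dates, but Step 4 shows that the imputation rules can also add drugs wrongly.
- A reader might infer that antipyretic and analgesic use after vaccination is what goes missing, so that the reactogenicity results are open to doubt. Protocol 4.2.1 delays dosing by at least 24 hours after such use. Post-dose use is therefore normally a new course; started after dose 1 and up to 28 days after dose 2, or in the 28 days after the booster, it is labelled C. The loss is mainly of long-term drugs and as-needed records left open.
- A reader might infer that the SAP wrongly omits the daily yes/no diary item on antipyretic and analgesic use. SAP 9.1.1 names no table of it. But the protocol says that the item is not an adverse event, and no objective or endpoint lists it. SAP 9 commits in general terms to summarizing safety data, and the table shells are not in the documents. No stated commitment is broken.
- A reader might scale the effect to an age cohort of 75. SAP 7.1 names no age split for these tables, and the SAP prevails where it differs from the protocol.

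**Conclusion.** The point holds as a minor defect in a derivation rule. Under Table 13-2, drugs in use before dose 1 or with no start date, and drugs begun in the gap before the booster, are missing from tables described as showing use after a dose. This follows from the stated rules and needs no assumption about the data.

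The size does depend on the data. The documents give no medication rates, so the number of participants affected is unknown and may be zero. The 4.0-point figure is a worst case; at planned sizes each omission is worth about 0.7 points in a priming arm and about 0.9 to 2.0 points in a booster group. The net direction is not fixed once dates are imputed. No endpoint, estimand or between-arm inference is called into question.

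**What to change.** In Table 13-2, classify a drug as concomitant for every dose window that its dates, after imputation, overlap, and let Prior and Concomitant apply together. Specifically:

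- A drug started before dose 1 and still in use on or after dose 1 is both Prior and Concomitant.
- A drug from the gap row is concomitant for the booster if its stop date is on or after the third injection.
- A completely missing start date counts as concomitant unless the drug stopped before the first injection.

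The cost is SAP wording and one derivation flag, using data already collected. The downside is that an open as-needed record may be counted in a window without use in it. Overcounts that come from imputed dates also remain. If the sponsor prefers to keep the start-date rule, the tables should be retitled as drugs started on study.

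A table of diary-reported antipyretic or analgesic use within 7 days of each dose would be a useful optional addition, since it would show actual use for that class of drug.

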7.2. Medical and Surgical Treatment Procedures

The number and percentage of participants with at least one medical and surgical treatment procedure during the priming vaccination period will be summarized for the Safety Analysis set.

Indication (i.e., Adverse Event vs. Other) and whether the treatment/procedure is ongoing or not will also be summarized by frequency.

All medical and surgical treatment procedures will also be presented in a data listing; for re-enrolled subjects, a separate data listing will be provided.

7.3. Vaccine Administration and Exposure

Study vaccinations will be summarized including the number and percentage of participants receiving each dose, whether administered per protocol or not, or not administered for the Safety set.

All study drug administration data will also be presented in a data listing.

Vaccine administration will be summarized and listed separately for re-enrolled subjects.

8. Immunogenicity Analysis

8.1. Primary and Secondary Immunogenicity Endpoints

For both primary and secondary endpoints blood sampling for immunogenicity testing will be drawn according to the schedule of events (Appendix 1: Schedule of Study Procedures).

8.1.1. Primary Immunogenicity Endpoint

To address the primary objective of the study the neutralizing antibody responses of ARCT-021 will be compared to placebo for the priming vaccination period. SARS-CoV-2 neutralizing antibody (NAbs) titer will be tested using pseudoviral microneutralization assay (Wuhan-Hu-1), and, if available, PRNT assay. If assays are available, additional strain-specific neutralizing antibody testing may be performed. Neutralizing antibody (NAb) responses will be evaluated on the mITT analyses set using the following estimands:

- Geometric Mean Titer (GMT) measured at all time points;
- Geometric Mean Fold-rise from baseline (GMFR); measured at all time points after baseline (= Day 0) (Estimand 2)
- Percentages of participants with ≥ 2 - and 4-fold increase in titer from baseline (Seroconversion [SC]) measured at all time points after baseline (Estimand 3).

